COVER PAGE

STUDY TITLE: Suture closure AFtEr VEIN access for cardiac procedures (SAFE-VEIN) Trial: A randomized, prospective study of the safety and efficacy of venous closure device compared to conventional closure strategies in post venous access procedures

NCT NUMBER: NCT04632641

VERSION DATE: 06/01/2022

Protocol Version Tracking Date: 06/1/2022

AURORA HEALTH CARE, INC.

PROTOCOL TITLE:

Suture closure AFtEr VEIN access for cardiac procedures (SAFE-VEIN) Trial: A randomized, prospective study of the safety and efficacy of venous closure device compared to conventional closure strategies in post venous access procedures.

PRINCIPAL INVESTIGATOR:

[name] [name] Electrophysiology [name] [contact] [contact]

I. Background and Rationale

Venous access is commonly used in interventional catheter procedures such as atrial fibrillation (AF) ablation, WATCHMANTM device placement, and Patent Foramen Ovale (PFO) closure. Access site bleeding and hematoma are anticipated vascular complications post procedure, and risk of complications may rise with a longer time to hemostasis (TTH). Two conventional method closure strategies (1) that are usually used for hemostasis in these procedures are:

- 1. figure 8 suture and
- 2. manual compression.

Using a vascular closure device to achieve hemostasis has been shown to shorten time to both hemostasis and ambulation as well as improve patient comfort and satisfaction (2). Perclose ProGlide Suture-Mediated Closure System (SMC) is a commonly used vascular closure device for arterial closure and is approved by FDA for percutaneous closure of femoral artery and vein access sites (3). Perclose ProGlide SMC has been shown to be safe with low incidence of vascular complication (3,4) and reduce the time to hemostasis (3). The device has been shown in a small study to lower the time to ambulation and shorten the length of stay compared to manual compression (5). To our knowledge, there have been no studies published that compare efficacy and safety of Perclose ProGlide SMC vs. figure 8 suture method.

II. Objectives and Specific Aim

Primary objective: To compare the safety and efficacy of closure strategies post venous access procedures in large-bore venous access procedures.

Hypothesis: We anticipate that the use of a venous closure device will decrease the time to hemostasis (TTH), time to ambulation (TTA) and time to discharge (TTD) compared to conventional methods of closure following venous access procedure.

III. Study Design & Methodology

This study will be a prospective, randomized study of patients who are undergoing one or more of the following procedures at ASLMC:

Large-Bore Procedures >13 F

- 1. WATCHMAN® device placement
- $2.\ Atrial\ fibrillation/flutter/SVT\ ablation\ using\ cryoballoon\ or\ laser\ balloon$
- 3. Leadless pacemaker
- 4. Pulmonary embolism thrombectomy (Inari FlowTriever system)
- 5. MitraClip transcatheter mitral valve repair

RANDOMIZATION:

Patients will be randomized into one of two venous closure groups after a clean stick has been achieved with no complications:

Large-bore (14F-25F) venous access group (1:1)
Perclose proglide smc
Figure 8 suture

Prior to enrollment a series of 110 randomization envelopes will be put together in a 1:1 to determine the closure strategy – Figure 8 suture or Perclose ProGlide SMC closure device for the large-bore procedures. Study investigators will draw an envelope to determine what group the subject will be randomized to only after sheath access has been achieved with no complications. Access should be ultrasound guided to guarantee a clean stick.

If randomization does not occur or if a complication not related to the Perclose ProGlide SMC closure device happens during the procedure the subject will be withdrawn from the study and considered a screen failure.

For both Perclose ProGlide SMC and figure 8 suture, supplemental manual compression may be used following device/suture placement if needed. If at any time the physician decides to use an alternate standard of care method as the primary method to achieve hemostasis other than that which the patient was randomized to, they may do so, and the patient will be considered a screen failure.

We will collect demographic data, past medical history, medication at the time of procedure, lab values at the time of procedure and post procedure, the need for blood transfusion, procedure details, and outcomes post procedure. *Study variables are listed in detail in the attached Excel file*.

Table 1: Schedule of Study Events:

Study Procedure	Screening	Day of Procedure	Follow-up (30 days post procedure)
Inclusion/exclusion	X		
Informed Consent		X	
Randomization to determine closure strategy		X	
Data collection (medical history/baseline demographics, medications, lab values, procedure details, and outcomes post procedure)		X	X

IV. Eligibility

Inclusion criteria:

Large-bore (>13F) Venous Access Procedures Inclusion Criteria:

All patients 18 years and older who are undergoing any of the following: WATCHMAN® device placement, atrial fibrillation ablation using cryoballoon or laser balloon, leadless pacemaker, Pulmonary embolism thrombectomy (Inari FlowTriever system), MitraClip transcatheter mitral valve repair at Aurora St. Luke's Medical Center from date of IRB approval through December 2022. All arterial line access should be radial.

Exclusion criteria:

Large-bore (>13F) Venous Access Procedures Exclusion Criteria:

- Patients in whom introducer sheaths >25F were used in the vein during the catheterization procedure.
- Patients with small femoral arteries or veins (< 5 mm in diameter).
- Patients with access sites in vascular grafts.
- Patients with intra-procedural bleeding around access site. Patients who cannot receive radial arterial line access.
- Patients who have complications during the procedure not related to the Perclose ProGlide SMC closure device
- The physician determines that they must use an alternate method as the primary venous closure method other than that which the patient was randomized to
- Active systemic or cutaneous infection, or inflammation in vicinity of the groin
- Pre-existing immunodeficiency disorder or chronic use of high dose systemic steroids
- Known history of bleeding diathesis, coagulopathy, hypercoagulability or platelet count < 100,000 cells/mm3
- Severe co-existing morbidities with life expectancy less than 12 months

- Femoral arteriotomy or femoral venotomy in < 10 days, or with any known vascular complications or residual hematoma, or with use of an intravascular closure device w/in previous 30 days
- Planned femoral venous or arterial access within next 30 days
- Unable to routinely walk at least 20 ft. without assistance
- LMWH within 8 hours before or after procedure
- Pregnant and/or lactating women
- Extreme morbid obesity (BMI > 40 kg/m2) or underweight (BMI < 20 kg/m2)

V. Subject Enrollment

Recruitment and consent are required since it is a prospective study. Patients will be identified for potential enrollment in this study from the lab schedules at Aurora St. Luke's Medical Center. The potential subjects medical record will be screened to determine eligibility. Patients found to be eligible will be considered for enrollment and may be contacted prior to the procedure to assess interest in participation.

VI. Specimen/Data Collection and Procedures

The source of data for this study will be the electronic medical record (Epic, Madison, WI). Only people included in this IRB will access the compiled data. Medical record information generated after the approval of this IRB will be collected up until the conclusion of the study.

VII. Risks, Protection & Benefits

Risks/adverse events as reported in the IFU – these complications may occur and/or be related to the procedure or the vascular closure:

- Allergic response
- Anemia
- Arterial stenosis/occlusion
- Arterio-venous fistula
- Bleeding from the puncture site
- Bruising/hematoma
- Death
- Device failure/malfunction/misplacement
- Device Entrapment
- Diminished pulses distal to closure site
- Hypotension/hypertension
- Edema
- Embolism
- Pulmonary Embolism
- Numbness
- Infection/sepsis
- Inflammatory response
- Intimal tear/dissection
- Ischemia distal to closure site
- Perforation of the vessel wall
- Nerve injury
- Pseudoaneurysm
- Retroperitoneal hematoma/bleeding
- Deep vein thrombosis
- Vascular injury
- Vasovagal episode
- Vasoconstriction/vasospasm
- Wound dehiscence
- Pain

• Thrombus formation

Risks of figure 8 suture method:

- Pain
- Pressure
- Hematoma
- Bleeding
- Vessel rupture
- Surgery

Benefits:

Depending on the closure strategy subjects may experience a decrease in bedrest time post procedure with potentially less complications.

Results of this study may also be generalizable to the larger healthcare community by informing standard of care guidelines for obtaining hemostasis and post procedure outcomes following the procedures studied in this protocol.

VIII. Adverse Event Reporting

Definitions

Adverse event: Any untoward medical occurrence, unintended disease or injury or untoward clinical signs in subjects, users, or other persons, whether or not related to the medical device.

Serious adverse event: Any adverse event that led to

- Death
- Life-threatening illness or injury
- Permanent impairment
- Prolonged hospitalization or change to inpatient status
- Requires medical or surgical intervention to prevent life-threatening illness or injury or permanent impairment
- Fetal distress, fetal death, or congenital abnormality or birth defect

b. Reporting Requirements

All observed or volunteered adverse events occurring from the time of randomization to 30-days post randomization will be recorded in the subjects' case histories, regardless of the study group or suspected causal relationship. For all adverse events, sufficient information will be obtained in order to permit: 1) adequate determination of the seriousness, and 2) causal relationship of the adverse event. Adverse events or serious adverse events found to be a result of the treatment regimen will be followed until resolution of the adverse event.

Reportable adverse events include:

- Excessive Bleeding
- Hematoma
- Ischemia
- Infection
- Rash at access site

All adverse events and serious adverse events are to be reported to the Aurora Health Care Internal Review Board as outlined in the applicable policies.

c. Assessment of Relationship

The Principal Investigator is responsible for assessing the relationship of the adverse event or serious adverse event to the treatment.

IX. Data Analysis and Review

Continuous variables will be presented as means and standard deviation or median and interquartile ranges if normality is not assumed. Baseline demographic and medical data will be summarized and compared by standard descriptive statistical methods (ANOVA for continuous variables and Chi squared test for categorical variables or their non parametric equivalents). Comparisons will be made among groups based upon clinical factors using univariate regression to select potential independent predictors of outcomes (as defined in section III of the current document). Relevant potential independent predictors as determined by univariate analyses and expert clinical knowledge will then be included in multivariate regression models. Assumptions and goodness of fit will be assessed for each model. Statistical significance will be defined as a two tailed p value < 0.048 at final analysis. Further data analysis will be performed by clinical statistician (TBD).

A stratified analysis by French size or procedure type will be considered if there is evidence to suggest one is needed.

An interim monitoring plan to perform periodic checks of the data after the first 25 subjects are enrolled and then again after 75 subjects are enrolled will be reviewed by the Biostatistician or study team to determine data integrity, accuracy, and consistency with the study objectives/hypotheses as well as preliminary analysis.

X. Statistical Considerations

A convenient sample size of approximately 55 subjects in each of the two randomized groups (Perclose ProGlide SMC and figure 8 suture) was determined to allow for parametric statistical methods. Following interim analysis: O'Brien-Fleming method was selected to adjust the p-value for interim analysis and final analysis. It was also used to calculate the required sample size at each stage of analysis in order to achieve 80% power in the outcome. Final sample size required was determined at 101 subjects. A 10% +/- should be added, to bring the total enrollment to 110 subjects.

XI. Outcomes

Primary outcomes: time to achieve hemostasis (TTH) and time to ambulate (TTA)

Secondary outcomes: time to discharge (TTD)/length of stay, post procedure major bleeding, mortality due to vascular complications, minor bleeding, access site hematoma, vascular thrombosis, vascular dissection, pseudoaneurysm, or AV fistula.

TTH: The elapsed time between "device" removal and first observed and confirmed venous hemostasis.

TTA: The elapsed time between removal of the final Perclose ProGlide SMC device (treatment arm) or removal of the final sheath (control arm), and the ability of subjects to stand and ambulate 20 feet without evidence of venous re-bleeding from the femoral access sites.

TTD/LOS: The elapsed time between removal of the final sheath, and the ability of subjects to be discharged. Length of hospital stay.

Major bleeding: Bleeding associated with ≥ 2 g/dl drop in hemoglobin level requiring transfusion, bleeding that occurs at a critical site, or bleeding contributing to death.

Minor Bleeding: Any bleeding that does not meet the criteria for major bleeding.

XII. Regulatory Requirements

Approval from the Aurora Health Care IRB will be obtained to perform this study, which includes approval of all associated informed consent forms. All protocol modifications and corresponding informed consent forms will be submitted for review and approval prior to implementing.

The Principal Investigator is responsible for ensuring that all study personnel have appropriate training and experience to perform the assigned duties.

The Principal Investigator will ensure that the study is performed in accordance with the approved protocol, and will document and report protocol deviations as required by the Aurora Health Care IRB policies.

XIII. Monitoring Plan

The goal of monitoring in this study is primarily to make sure that the primary data are collected and recorded properly, and consenting process was done.

The Principal Investigator will be responsible for monitoring the safety environment of the participants, and will ensure that

- a) Only subjects who meet the study eligibility criteria will be enrolled. All subject inclusion/exclusion criteria were reviewed and verified with source documents, when applicable.
- b) The informed consent process will be obtained prior to proceeding with any study procedures. Any problems with informed consent will also be documented, and reported to the IRB, if required.
- c) Data is collected and analyzed as specified in the protocol.
- d) Adverse events are reviewed promptly and reported as required.
- e) Privacy and confidentiality of subjects is maintained. Consent forms will be stored in a room accessible only to research personnel.

- f) Subject withdrawals will be documented for the reason of withdrawal.
- g) Subjects will be informed during the informed consent process that study results may be disseminated in the form of presentations at conferences and publications in journals. The data/results that will be presented will only include anonymous/aggregate data, nothing that will identify subjects.
- h) A regulatory binder will be kept to document: IRB approvals, protocol versions, informed consents (all versions), all formal communications with the IRB (approval letters, acknowledgements), Delegation of Authority Log.

XIV. References

- 1. U. Lakshmanadoss et al. Figure-of-eight suture for venous hemostasis in fully anticoagulated patients after atrial fibrillation catheter ablation. Indian Pacing and Electrophysiology Journal 17 (2017) 134e139
- 2. PMA P960043/S097: FDA Summary of Safety and Effectiveness Data

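### Safety is part of the primary objective but has no primary or composite outcome, and for uncommon events the p < 0.048 criterion at 55 per arm cannot answer it

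*Combined protocol and SAP*

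**What the plan says.** Section II states the primary objective as "To compare the safety and efficacy of closure strategies post venous access procedures in large-bore venous access procedures". The hypothesis that follows covers only time to hemostasis (TTH), time to ambulation (TTA) and time to discharge. It gives no direction or criterion for safety.

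Section XI has "Primary outcomes: time to achieve hemostasis (TTH) and time to ambulate (TTA"). Safety appears among the secondary outcomes, after time to discharge/length of stay: "post procedure major bleeding, mortality due to vascular complications, minor bleeding, access site hematoma, vascular thrombosis, vascular dissection, pseudoaneurysm, or AV fistula". That is eight items, with no composite, ranking, margin or expected rate.

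Section IX gives one decision criterion: "Statistical significance will be defined as a two tailed p value < 0.048 at final analysis". The only categorical test it names is the "Chi squared test for categorical variables or their non parametric equivalents", and it names this for baseline data. Outcomes go to univariate and then multivariate regression of unstated type, and further analysis is left to a statistician not yet named.

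Section X has "A convenient sample size of approximately 55 subjects in each of the two randomized groups", later linked to a calculation "in order to achieve 80% power in the outcome". It does not say which outcome.

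Section VIII has all adverse events recorded from randomization to day 30 in both groups, but attaches no between-arm comparison to them.

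**The concern.** Safety is named alongside efficacy in the primary objective, yet the plan gives it no outcome, estimate or precision target on which an answer could rest. What remains is a significance threshold applied to eight separate events in about 110 patients. For an uncommon event, that threshold is seldom crossed even when the true risk differs materially between arms, so a non-significant result carries little information about safety.

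The stake is what the trial can say at the end. Section I says that no published study known to the authors compares this device with the figure 8 suture on efficacy and safety. Section VII hopes that the results may inform standard-of-care guidelines. Without a planned safety estimate, the safety half of the objective would rest on results that cannot separate no difference from a doubling.

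**Working it through.** **Inputs from the documents.** About 55 per arm (Section X), 1:1 allocation (Section III), two-sided 0.048 at the final analysis (Section IX), eight safety items (Section XI).

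**Assumed.** Control event rates. The documents give none, so a range is shown.

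**The plan's own figure.** Section X gives 101 subjects for 80% power, raised to 110. The 101 cannot be rebuilt because the outcome, effect size and standard deviation are not stated. Read as a comparison of two means with 50.5 per arm, it corresponds to a standardized difference of (1.977 + 0.842) × √(2/50.5) = 0.56. The inflation is roughly consistent: 101 × 1.1 = 111.1, against 110 stated. None of this bears on a safety event.

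**Power to detect a doubling of one event.** For control rate p and device rate 2p, power is the sum of Bin(i; 55, p) × Bin(j; 55, 2p) over all tables (i, j) with p-value < 0.048. The plan names no test for safety events, so two are shown.

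| Control vs device | Expected events | Fisher exact | Uncorrected chi-squared |
|---|---|---|---|
| 1% vs 2% | 0.6 vs 1.1 | <0.1% | 1.5% |
| 2% vs 4% | 1.1 vs 2.2 | 0.8% | 6.4% |
| 3% vs 6% | 1.6 vs 3.3 | 2.7% | 10.1% |
| 5% vs 10% | 2.8 vs 5.5 | 7.5% | 15.9% |
| 10% vs 20% | 5.5 vs 11.0 | 22% | 31% |
| 15% vs 30% | 8.2 vs 16.5 | 38% | 48% |
| 20% vs 40% | 11.0 vs 22.0 | 56% | 64% |
| 25% vs 50% | 13.8 vs 27.5 | 72% | 78% |

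Power passes 50% at a control rate of about 16% (chi-squared) to 18% (Fisher), and 80% at about 26% to 28%. For 80% power to detect a doubling, the normal-approximation formula needs 1,156 per arm at 2%, 440 at 5% and 202 at 10%. A tripling from 5% to 15% has 28% (Fisher) to 42% (chi-squared) power.

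**What sparse results would mean.**
- With 0/55 in one arm, Fisher needs at least 6/55 in the other: 5 vs 0 gives p = 0.057 and 6 vs 0 gives p = 0.027.
- The exact 95% upper limit for 0/55 is 1 − 0.025^(1/55) = 6.5%.
- The chance that at least one arm has no event, with rate p in both arms, is 2(1−p)^55 − (1−p)^110. This is 55% at 2% and 34% at 3%. If the regression is ordinary logistic, an empty arm leaves the odds ratio without a finite estimate.

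**Precision if safety is estimated instead.** With equal counts in the two arms, the Newcombe half-width is √[(p−l)² + (u−p)²], where l and u are the Wilson limits.
- 2/55 in each arm: p = 0.036, limits 0.010 and 0.123, half-width √(0.026² + 0.087²) = 0.091, about ±9 points.
- 5/55 in each arm: p = 0.091, limits 0.039 and 0.196, half-width √(0.051² + 0.105²) = 0.117, about ±12 points.

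**The case against.** **Rarity is not documented for all eight events.** A reader might infer that every listed safety event is rare. The documents do not support that. Section I speaks of a low incidence of vascular complications with the device, but it also calls access-site bleeding and hematoma anticipated. Section XI counts all non-major bleeding as minor. If either event has a control rate above about 16% to 18%, a doubling would more likely than not be detected. This stands, and it limits the point to lower-rate events.

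**The claim is per event.** A reader might infer that all eight results would be non-significant whatever the truth. If all eight doubled independently, the chance of at least one p < 0.048 is 1 − (1 − power)^8. That is 0.4% to 11% from 1% control rates and 47% to 75% from 5%. Independence is an assumption, but the wider claim fails. One significant result out of eight would still be hard to interpret, because the plan has no multiplicity rule.

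**The plan does not commit the misreading.** A reader might infer that non-significance will be presented as comparable safety. Nothing in the documents says so. The hypothesis makes no safety claim, and Section IX leaves further analysis open. This stands: the defect is that nothing in the plan prevents that reading or offers a better answer.

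**Other safety data exist.** Adverse events to day 30 are recorded in both arms, and the detailed variable list is in a separate file that is not part of the documents. No between-arm comparison is specified for the adverse events, so they do not fill the gap.

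**Conclusion.** The point holds in limited form. Safety is part of the primary objective, but it has no primary or composite outcome, margin, precision target or stated power. The only criterion given is two-tailed p < 0.048. For a single event with an assumed control rate of 10% or less, power to detect a doubling is at most about 31%. The chance of a non-significant result despite a true doubling is therefore at least 69%; it is 84% to 92% at 5% and 94% to 99% at 2%. Such a result cannot answer the safety objective.

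This rests on assumed rates, on 55 evaluable patients per arm and on a two-group comparison, since the plan names no test for safety events. The choice between Fisher and chi-squared changes the figures but not the conclusion at these rates. It does not extend to events with control rates near 20% or above, which may include minor bleeding or hematoma. The TTH and TTA analyses are unaffected. The change is worth making because it is cheap, and the objective as written cannot otherwise be met.

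**What to change.** 1. **Section XI.** Define one patient-level safety outcome from items already listed: any access-site or vascular complication to day 30, meaning major bleeding, hematoma, thrombosis, dissection, pseudoaneurysm, AV fistula, or death from a vascular complication. Report minor bleeding separately, or in a sensitivity version that includes it, so that a frequent mild event does not dominate the composite. Two boundaries need a sentence each: whether a hematoma short of major bleeding counts in its own right, and whether major bleeding at a critical site away from the access site counts.

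2. **Section IX.** Report this outcome by randomized arm as a risk difference with a 95% score or exact interval, and give component counts descriptively. Count every randomized patient. Sections III and IV would withdraw patients as screen failures for a complication unrelated to the device or for a change of closure method. Dropping them after randomization could remove the very events that the comparison is about.

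3. **Section II.** State that efficacy is tested and safety is estimated, and that a non-significant difference will not be reported as equivalent safety.

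**Cost.** Protocol and SAP wording, with no new type of data. Day-30 outcomes must be kept for randomized patients whom the plan would now withdraw. Section VIII already has adverse events recorded from randomization to day 30. The downside is a more modest safety claim with a wide interval, about ±9 points at 2/55 per arm and ±12 at 5/55.

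### Allocation is weakly protected: investigators draw from 110 envelopes with no stated order, independent holder or log, and patients can leave as screen failures once the arm is known

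*Combined protocol and SAP*

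**What the plan says.** The allocation procedure is in section III, under Randomization. "Prior to enrollment a series of 110 randomization envelopes will be put together in a 1:1 to determine the closure strategy". Then "Study investigators will draw an envelope to determine what group the subject will be randomized to", and this happens "only after sheath access has been achieved with no complications". No section says how the sequence is generated, who prepares or holds the envelopes, whether they are sealed, opaque or numbered, whether they are used in order, or whether openings are recorded.

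The same section gives two exits that can apply after the draw:

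- Removal from the study, counted as a screen failure, under the rule that begins "If randomization does not occur or if a complication not related to the Perclose ProGlide SMC closure device happens during the procedure the subject will".
- If the physician chooses another standard method as the primary closure, "they may do so, and the patient will be considered a screen failure".

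Section IV repeats the second exit as an exclusion criterion: "The physician determines that they must use an alternate method as the primary venous closure method other than that which the patient was randomized to".

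Section XI ends time to hemostasis (TTH) at an observed and confirmed event and names no blinded assessor. Section XIII asks for the reason for each withdrawal to be documented but does not mention envelopes.

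**The concern.** In a single-center trial whose two closures look different to the person applying them, and with no blinding described, concealed allocation is the main protection against selection bias. Here the draw comes after access, when the investigator already knows the procedure, the sheath and how access went. That timing keeps the arm from influencing the puncture. It does not stop knowledge of the patient from influencing the allocation if the envelopes are not in a fixed, recorded order. The hypothesis in section II is also directional, favoring the device.

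The exit rule is the firmer half of the point, because it is written policy. A patient whose assigned method is set aside after the envelope is opened leaves the study. If that happens more often in one arm, or for harder patients in one arm, the groups compared are no longer those formed by randomization. The complication exit is worded around one arm's device, so read literally it does not treat the two arms alike. TTH and time to ambulation (TTA), the primary outcomes, would be affected directly.

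**Working it through.** **Inputs.** From the documents: 110 envelopes at 1:1, so 55 per arm if exactly balanced (section III); final two-sided level 0.048 (section IX); required N of 101, 80% power, total enrollment 110 (section X). The documents give no effect size, SD, steering rate or prognostic effect, so those below are assumptions.

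1. **The plan's own figure.** 101 × 1.10 = 111.1 and 101 / 0.90 = 112.2. Both are within 3% of the stated 110. The 101 cannot be rebuilt without an effect size. Worked backwards for two means at level 0.048 and 80% power, it implies a standardized difference of about (1.977 + 0.842) × √(4/101) = 0.56 SD. This serves only as a yardstick.

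2. **Foresight from counting.** For one balanced set of 2n envelopes, the best guesser expects n + 2^(2n−1)/C(2n,n) − 1/2 correct. With n = 55 this is 55 + 6.59 − 0.5 = 61.1 of 110, or 55.5% against 50% by chance. On average only about the last 2 assignments are certain. Small blocks would raise this (70.8% for blocks of 4, 65.3% for blocks of 10), but the protocol mentions no blocks.

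3. **Steering between arms.** Assume no true effect, 55 per arm, normal outcomes, and a few patients who are slower by s SD. If k1 of them fall in one arm and k0 in the other, bias = s(k1 − k0)/55. Simulated type I error at nominal 4.8% (40,000 runs per case):

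| Slower patients in one arm | s | Bias (SD) | Type I error |
|---|---|---|---|
| 4 of 4 | 0.5 | 0.5 × 4/55 = 0.04 | 5.0% |
| 4 of 6 | 1 | (4 − 2)/55 = 0.04 | 4.7% |
| 8 of 11 | 1 | (8 − 3)/55 = 0.09 | 6.1% |
| 6 of 6 | 1 | 6/55 = 0.11 | 7.9% |
| 11 of 11 | 0.5 | 0.5 × 11/55 = 0.10 | 7.5% |
| 11 of 11 | 1 | 11/55 = 0.20 | 15.6% |

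The two cases with a bias of 0.04 SD are about nominal. The last row, 0.20 SD, is roughly a third of the 0.56 SD yardstick.

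4. **Loss after the arm is known.** The table does not model this. Suppose each arm of 55 holds m patients who are s SD slower and j of them leave one arm as screen failures. The bias is s[m/55 − (m − j)/(55 − j)]. With m = 6 and s = 1: j = 3 gives 6/55 − 3/52 = 0.109 − 0.058 = 0.05 SD, and j = 6 gives 0.11 SD.

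5. **Supply.** There are exactly 110 envelopes for 110 enrollments. Each screen failure after opening uses one, and no replacement rule is given. The margin over the required 101 is 110 − 101 = 9.

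**The case against.** The strongest reply is that this is a reporting gap. The text speaks of a series of envelopes, which fits an ordered stack, and good envelope practice may exist at the site without being written down. That is fair. The absence of an order and a log is an omission, and silence about opacity or sealing alone would be missing detail.

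A reader might go further and infer several things that the documents do not support:

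- **That following the protocol allows a redraw.** It does not. One envelope determines the group, a second draw would be a deviation, and section XII requires deviations to be documented and reported.
- **That patients can be dropped without a trace.** Section XIII(f) requires reasons for withdrawal, and unused envelopes could be counted. However, no one is assigned that count, and without a log an opened envelope is not tied to a patient.
- **That assignments can be foreseen.** Counting alone gives 55.5%. More would need see-through envelopes or small blocks, and neither is documented.
- **That the investigator who draws also performs the closure and judges hemostasis.** This is a reasonable inference from a draw made during the procedure, but it is not stated. Outcome assessment is in any case a separate problem that concealment would not cure.
- **That the analysis could never reveal steering.** Section IX plans baseline comparisons and multivariable models, which could pick up steering on recorded factors. Steering on unrecorded judgement would escape them.

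The exit rule survives all of this. Losing a patient after the arm is known is permitted by sections III and IV and needs no breach of the protocol.

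**Conclusion.** The point holds in a limited form. The stated draw leaves allocation weakly protected, and the stated exit rule permits arm-dependent loss of randomized patients. There is no evidence in the documents that steering happened.

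The size cannot be fixed from the documents. Under assumed steering, the type I error runs from about nominal (4 of 6 patients who are 1 SD slower in one arm) to about 8% (all 6) and about 16% (all 11 of 11). The last two require every slower patient to land in one arm, so a reader should not take 16% as the expected error. The case for action rests on the stated rules and the low cost of replacing them, not on that figure. This should be changed, but it does not show that the comparison is already invalid.

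**What to change.** For all remaining patients, replace the draw with wording to this effect: envelopes are opaque, sealed and consecutively numbered, made from a computer-generated list by someone not involved in the procedures; the next number in sequence is assigned; study ID, date and time are written on the envelope before it is opened; every opening is logged and reconciled against the list. The remaining envelopes must be remade, since relabelling would leave contents already fixed under the present method.

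Replace the two post-assignment screen-failure rules in section III, and the matching criteria in section IV, with this: every patient whose envelope is opened counts as randomized, is followed, and is analysed in the assigned arm. This need not restrict the physician's choice of closure.

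The change cannot protect patients already randomized, and section X refers to an interim analysis that has already taken place. So also report how many envelopes have been opened to date and what happened to each.

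Cost: a new set of envelopes, a short log, a few minutes in the lab and a protocol amendment. Keeping patients closed by another method dilutes the contrast slightly. If 5% of one arm (assumed) had outcomes typical of the other arm, a 0.56 SD difference would become 0.95 × 0.56 = 0.53 SD.
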